### Variables and measures

Variables are collected in electronic case report forms (CRFs) as in figure 1 and table 1. CRF 1 and 2 are divided into section A and B with variables in A related to liver surgery and in B to breast oncology. CRF 3 and 4 is only for those randomized to local treatment.

CRF1		Registration. Ca 15-3. Performance status. Somatic comorbidities.				
		1a BCLM characteristics				
		1b Breast cancer characteristics and. Oncological and surgical breast cancer treatment of prior to inclusion.				
CRF2		2a Liver metastases after oncological treatment. Evaluations of response according to RECIST 1.1 (9).				
		2b Oncological treatment after inclusion.				
		2c. Result of randomization.				
	Only for thos	se randomized to local treatment				
	CRF3	Local treatment.				
	CRF4	Complications (30-day) according to Clavien-Dindo and the CTC 4.03 scale. Pathological anatomical diagnosis of liver metastases including ER, PgR, Her2. Total number of days at hospital.				
CRF5	Follow up 3, 6, 9, 12, 18, 24, 30, 36 months (5a-h). Oncological treatment and grading of complications by the CTC 4.03 scale. Secondary intervention against metastases. Performance score. Quality of life 3, 12 and 24 months.					
CRF6	Recurrence. Progression.					
CRF7	End of study. Vital status.					

For survival analyses, the primary endpoint is time from randomization to death from any cause. Secondary endpoints are three years overall survival, progression free survival, breast cancer specific survival and median overall survival. Disease progression will be evaluated at each radiology control. This analysis cannot be blinded since radiologists can see signs of previous liver resections. Survival will primarily be evaluated in an intention to treat manner and secondary in a per protocol analysis.

To study safety and complications, 30-days and 90-days mortality after surgery will be determined and complications will be described and graded by the Clavien-Dindo score. Chemotherapy toxicity will be graded by the CTC 4.03 scale.

To study predictive factors, patient related factors (age and comorbidity), primary tumour related factors (size, histology, molecular subtype) and factors related to the metastatic disease (number, size, locations, molecular subtype, response to treatment, disease free interval) will be related to survival. Hormonal receptor status will enable characterization of the molecular subtype of the primary tumour. To predict outcome, they will be classified according to the St Gallen classification; Luminal A, Luminal B (HER2-positive), Luminal B (HER2-negative), HER2- enriched (non- luminal) and triple-negative breast cancer.

Quality of life will be registered by EORTC QLQ-C30 and QLQ-LMC21 at inclusion, and follow up 3, 12 and 24 months after randomization. QLQ-LMC21 will be added to the study when available in Swedish.

STUDY PLAN	Breast Cancer MDT	1st visit info	1st Liver Surgery MDT	Oncol. treatm.	2nd Liver Surgery MDT	Local treatm. or oncol. treatm.	Postop visit	Follow up 3 months	Follow up 6, 9, 12 months	Follow up 18, 24, 30, 36 months
Time					0			3	6, 9, 12	18, 24, 30, 36
Admission		X		X		X	Х	х	X (12m)	X (24m, 36m)
Randomization					Х					
CRF		1			2	3	4	5 (6, 7)	5 (6, 7)	5 (6, 7)
Informed consent and inclusion		Х								
Randomization					Х					
MRI liver, liver contrast		x			x					
CT thx- abdomen		x			x	X (only liver and only post ablation)		x	x	x
PET-CT		х				, í				
RECIST 1.1					Х					
CA 15/3 (recom- mended)	x					X		X	X (12M)	X (24M)
Biopsy of metastasis	Х									
Histology	х					X (surgery)				
QoL EORTC QLQ C30		X						x	X (12M)	X (24 M)

Table 1.

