## **Research questions**

- Is there a survival benefit of local treatment of BCLM by liver resection, ablation or stereotactic radiotherapy, compared to oncological treatment only? We will primarily compare time to death from any cause and calculate the hazard ratio in each arm, adjusted for known predictive factors. Secondary endpoints are three years overall survival after randomization, median overall survival, progression free survival and breast cancer specific survival.
- 2. What is the complication rate for each treatment and what kind of complications arise? 30-days and 90-days mortality after surgery will be determined and complications will be described and graded by the Clavien-Dindo score. Chemotherapy toxicity will be graded by the CTC 4.03 scale.
- 3. What are the predictive factors for survival after surgical and/or oncological treatment of BCLM? Predictive factors for survival (described on page 4) will be analyzed in a cox proportional hazards model.
- 4. How is quality of life influenced in BCLM patients after surgical treatment compared to oncological treatment? EORTC QLQ-C30 and QLQ-LM21 will be followed at inclusion, and follow up 3, 12 and 24 months after randomization. Quality of life will be analyzed using an ordinal proportional odds regression model.

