stopped and participants in the control arm will be allowed to cross over. If the study reaches a non-significant result in the end of the study it may be prolonged according to a new power calculation and a second ethical review.

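### CRF3 and CRF4 follow the randomised arm, not the treatment received, so procedure details and 30-day Clavien-Dindo data are not collected for controls who have local liver treatment

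*Protocol*

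**What the plan says.** The Variables and measures section of the protocol sets the rule in its text, "CRF 3 and 4 is only for those randomized to local treatment", and repeats the restriction as a sub-heading in the CRF list. CRF3 describes the local treatment. CRF4 holds "Complications (30-day) according to Clavien-Dindo and the CTC 4.03 scale", together with the pathology of the liver metastases and the days in hospital.

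The later forms carry no arm restriction. CRF5, at 3, 6, 9, 12, 18, 24, 30 and 36 months, includes "Oncological treatment and grading of complications by the CTC 4.03 scale" and "Secondary intervention against metastases". CRF7 is described as "End of study. Vital status".

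Item 2 of the Research questions asks "What is the complication rate for each treatment and what kind of complications arise". The matching commitment in Variables and measures is that "30-days and 90-days mortality after surgery will be determined and complications will be described and graded by the Clavien-Dindo score".

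Estimated sample size and power adds that, if the primary endpoint is reached at the interim analysis and the study is stopped, "participants in the control arm will be allowed to cross over".

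**The concern.** The safety question is put per treatment, but the forms that answer it for local treatment are opened by allocation. If a control participant later has a local liver procedure, no form is specified for what was done, its 30-day Clavien-Dindo grade, the pathology or the hospital stay.

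A table of complications by treatment received would then lack those procedures, which come later in the disease course than the ones in the randomised arm. A later analysis plan can choose how to tabulate data, but it cannot recover grades and procedure details that were never collected. The trigger therefore has to be right in the protocol and the electronic CRF.

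**Working it through.** **1. Which form covers which item for a control participant who has local treatment** (CRF list in Variables and measures)

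| Item | Form that holds it | Open to a control? |
|---|---|---|
| Details of the local procedure | CRF3 | No |
| 30-day Clavien-Dindo grade | CRF4 | No |
| Pathology of treated metastases, hospital days | CRF4 | No |
| Fact of a secondary intervention | CRF5 | Yes |
| CTC 4.03 grades at scheduled visits | CRF5 | Yes |
| Vital status | CRF7 | Yes |

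CRF5 does not replace CRF4. It lists no Clavien-Dindo item. Its visits are 3 months apart in the first year and 6 months apart afterwards, so no visit is tied to a 30-day postoperative window. Mortality at 30 and 90 days needs the date of surgery as well as vital status, and the protocol does not say whether the CRF5 entry records that date. Table 1 places CRF3 and CRF4 once, at the treatment step and the postoperative visit before the 3-month follow-up, so a later procedure has no slot.

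**2. Size if the trial runs as planned**

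With 100 participants per arm and y controls who have local treatment, the share of treated participants without CRF3 and CRF4 is y/(100 + y), if everyone in the local arm is treated. The documents give no value or rate for y, so this share cannot be computed.

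**3. Upper scenario after an interim stop**

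Inputs from the protocol: interim after 100 inclusions, 1:1 allocation (50 controls), 35 inclusions per year, 30% three-year survival in controls.

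Assumptions: uniform accrual, exponential survival, all 100 randomised, all 50 in the local arm treated.

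- Control hazard: λ = −ln(0.30)/3 = 0.401 per year.
- Accrual time: T = 100/35 = 2.86 years. Treatment before randomisation lasts two months (chemotherapy) or three (hormonal); taking off the midpoint of 2.5 months (0.21 years) gives 2.65 years.
- Proportion of controls dead at the interim: 1 − (1 − e^(−λT))/(λT).
  - T = 2.65: λT = 1.063, so 1 − 0.655/1.063 = 0.384.
  - T = 2.86: λT = 1.147, so 1 − 0.682/1.147 = 0.405.
- Between 38% and 41% would have died, which leaves about 30 of 50 alive.
- All 30 cross over: 30/(30 + 50) = 30/80 = 38%.
- Half cross over: 15/(15 + 50) = 15/65 = 23%.

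With x crossovers the share is x/(50 + x), which falls towards zero as x falls. Both figures assume high uptake. Randomisation required stable or responding disease, and entry required 1–4 lesions amenable to surgery and no non-skeletal extrahepatic disease; some surviving controls would no longer fit that description.

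**The case against.** The strongest defence is that CRF3 and CRF4 document the index procedure given by protocol, as their place in Table 1 suggests, and that later interventions in either arm belong on CRF5. On that view the complication rate in the randomised local-treatment arm is a coherent safety estimate, and procedures in controls concern a different, later population whose tabulation can be left to the analysis plan. Much of this stands: leaving out control procedures does not distort the by-arm rate. It does not remove the point, because the question is asked per treatment and tabulation cannot supply a grade that no form collects.

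Several stronger readings are tempting and not supported:

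- **Local treatment in controls disappears from the safety data.** It does not. CRF5 has no arm restriction and can hold both the intervention and CTC-graded complications, and CRF7 records vital status.
- **Crossover is a planned part of the trial.** It is permitted only if the primary endpoint is reached at the interim and the study is stopped. The protocol does not say which forms would then apply, so extending the arm restriction to that period is a reading of the rule as written.
- **CRF5 shows that local liver treatment of controls is expected.** Its secondary-intervention entry names neither the control arm nor the liver. It leaves room for such treatment but gives no expectation of how often.
- **The per-protocol analysis is compromised.** That analysis mainly needs the fact and timing of treatment. The protocol only summarises the forms, so whether CRF5 records type and date cannot be seen.

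**Conclusion.** The point holds as a cheap improvement of modest importance. The trigger for CRF3 and CRF4 is stated twice and rests on allocation. Followed as written, it leaves controls who have local liver treatment without procedure details, 30-day Clavien-Dindo grade, pathology or hospital days, although the safety question is asked for each treatment.

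The size is unknown. Without an interim stop the gap is limited to secondary interventions and may be small. A reader might take 23–38% as the expected loss; it is an upper scenario that depends on an early stop, on the survival and accrual assumptions above, and on half to all of the surviving controls being suitable for local treatment and taking it.

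**What to change.** Replace the restriction, in both the text and the CRF list of Variables and measures, with a rule that CRF3 and CRF4 are completed for every local treatment of liver metastases (resection, ablation or SBRT) in either arm, with the date of treatment and the allocated arm. State that this includes any crossover after an interim stop, and note under Table 1 that a later procedure opens the same two forms.

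Report complications and 30- and 90-day mortality by treatment received, beside the table by randomised arm.

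The cost is one change of trigger in the electronic CRF and a few extra forms for controls who have a local treatment. No visit or procedure is added.

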## Material: Patient selection

Inclusion will start in all six regional cancer centres in Sweden.

Inclusion criteria	
 
§ Signed informed consent
 
§ >18 years old
 
§ ECOG 0-1
 
§ Breast cancer history
 
§ Breast cancer liver metastasis verified by biopsy
 
§ Patient amendable for liver surgery and pre- and postoperative oncological treatment
 
§ 1-4 liver metastasis amendable to surgery with functional liver remnant volume >30%
 

Exclusion criteria	
 
§ Previous or present non-skeletal extrahepatic disease
 
§ > 4 liver metastases on preoperative or previous examination
 
§ Pregnancy
 
§ Progression of disease upon oncological treatment
 

Participants will be randomized by an oncologist at a study centre. Participants will be stratified on study centre. Randomization and stratification will be computer-based and administered upon the study website. The 1:1 allocation of participants into groups will be performed in random blocks, with random block sizes of 2 to 6. The study website will apply the Pheedit system and provide electronic CRFs. Each site coordinator will have access to the website and will be able to include and randomize participants. Non-participants who fulfill inclusion criteria will be registered by date, initials, clinic and date of birth.

### Estimated sample size and power

Based on preliminary results from a nationwide retrospective study (7) and the most recent case series, we assume that the overall 3-year survival to be approximate 40% averaged across both groups. Mariani et al (5) conducted a case control study of a population similar to the inclusion criteria in this study and detected RR 3.04 (CI: 1.87-4.92) in a multivariate cox regression analysis in favour of liver surgery. A smaller reduction of risk is clinically relevant but the challenge of this study is to recruit participants. In order to reach a power of 80 % to detect a hazard ratio of 1.9 with a significance level of 0.05, 190 study participants are required. Under the assumption of a drop-out rate of 5%, we therefore intend to include 200 participants in total. The sample size calculation is made assuming an unadjusted analysis. In the analysis of the primary outcome, model adjustments for baseline covariates will be made (age, molecular subtype of primary tumour, TNM-stage of primary tumour, disease free interval, single or multiple BCLM and presence of bone metastases yes/no). As these covariates are well known prognostic factors, we expect this to give additional gain in power or equivalent opportunity to detect smaller hazard ratios (8). Based on results from a nationwide retrospective study (7) and the most recent case series we assume that the secondary endpoint 3-years survival will be 30% in the control arm (oncological treatment only) and 50% in the treatment arm (surgery and oncological treatment). To reach 80% power with a 5% drop out rate and a level of significance p<0.05, the total study population is calculated to 200 participants also in this analysis.

Isolated oligometastases in the liver affect about 5% of those with advanced breast cancer. This corresponds to 70 patients per year in Sweden. We assume that we can include 50% of these, thus 35 per year. The study will be open for recruitment from centres outside of Sweden with a further specified protocol for surgical and oncological treatment and additional ethical review.

The study will be open for recruitment during 8 years and participants will be followed for at least 3 years. Interim analyses will be performed by the safety committee after inclusion of 100 participants. If the primary endpoint is reached at the interim analysis, the study will be

stopped and participants in the control arm will be allowed to cross over. If the study reaches a non-significant result in the end of the study it may be prolonged according to a new power calculation and a second ethical review.

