### **Statistical methods**

The primary outcome, time to death for any cause, will be visualized in a Kaplan-Meier plot and analyzed using Cox proportional hazard regression. The null hypothesis to be tested is that the hazard for the intervention group is equal to the hazard of the control group, in a twosided test. A random effects model will be applied with study centre as random effect. Adjustments will be made for age, molecular subtype of primary tumour, TNM-stage of primary tumour, disease free interval, single or multiple BCLM and presence of bone metastases (yes/no) for the purpose of increasing precision and statistical power in analysis. Age will be modelled as a continuous variable using natural cubic splines with three nodes distributed at the 10th, 50th and 90th percentile of the age distribution to account for nonlinear effect. The significance level will be set at 0.05.

Three years survival will be analyzed using logistic regression, adjusted for the same covariates as above,

Progression free survival and breast cancer specific survival will be analyzed using cox regression, as described for the primary outcome.

Predictive factors for survival will be analyzed in a cox proportional hazards model. Quality of life will be analyzed using a ordinal proportional odds regression model.

[name] and statistician at Registercentrum Norr, will be responsible for the statistical analysis plan.

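### The stated 190 participants for 80% power at a hazard ratio of 1.9 do not follow from the protocol's own 40% three-year survival; 190 matches 40% taken as mortality

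*Protocol*

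**What the plan says.** All the planning figures are in the protocol section Estimated sample size and power.

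- Survival assumption: "we assume that the overall 3-year survival to be approximate 40% averaged across both groups".
- Primary-endpoint requirement: "reach a power of 80 % to detect a hazard ratio of 1.9 with a significance level of 0.05, 190 study participants are required".
- Drop-out: "Under the assumption of a drop-out rate of 5%, we therefore intend to include 200 participants in total".
- Basis of the calculation: "The sample size calculation is made assuming an unadjusted analysis".
- Secondary endpoint, sized separately: "3-years survival will be 30% in the control arm (oncological treatment only) and 50% in the treatment arm", which again leads to a total of 200.
- Follow-up: "The study will be open for recruitment during 8 years and participants will be followed for at least 3 years".

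Two further inputs are given elsewhere. Statistical methods sets the null hypothesis that "the hazard for the intervention group is equal to the hazard of the control group, in a twosided test". Material: Patient selection fixes the ratio: "The 1:1 allocation of participants into groups will be performed in random blocks".

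No number of deaths, death probability or formula is given for the primary endpoint.

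**The concern.** For a time-to-event endpoint, power depends on the number of deaths. The number of participants is that number divided by the probability of dying during follow-up. The protocol's only mortality information for this step is 40% survival, so 60% should be the divisor. The stated 190 is what a divisor of 40% gives.

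This is the sample-size justification for the primary endpoint. The same paragraph concedes that a smaller risk reduction would be clinically relevant and that recruitment is the difficulty. Both sides of that trade-off are misstated: on the protocol's assumptions, either far fewer participants suffice for a hazard ratio of 1.9, or the planned number can detect a clearly smaller effect. The section also allows prolongation after a non-significant result on the strength of a new power calculation, and that calculation should not start from a wrong base.

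**Working it through.** **Inputs.** Hazard ratio 1.9, power 80%, significance level 0.05, 190 participants before drop-out, unadjusted analysis, 40% average three-year survival (Estimated sample size and power); two-sided test (Statistical methods); 1:1 allocation (Material: Patient selection). Normal quantiles: 1.960 and 0.842.

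**Step 1: deaths required (Schoenfeld, 1:1).**
D = 4(1.960 + 0.842)² / (ln 1.9)² = 4 × 7.849 / 0.4120 = 76.2, or 77 rounded up.

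**Step 2: reproduce the stated 190.**
- Probability of death 0.40: 76.2/0.40 = 190.5. This is the stated figure.
- Drop-out: 190/0.95 = 200. This step is correct, and it shows that drop-out is not already inside the 190.

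**Step 3: use the stated assumption.** The word used is survival, and the arm-specific figures confirm it: (30% + 50%)/2 = 40%. So the probability of death by three years is 1 − 0.40 = 0.60.
- 76.2/0.60 = 127.0; from 77 deaths, 77/0.60 = 128.3, or 129.
- With 5% drop-out: 135 to 136.

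**Step 4: can another standard method give 190 at 60% mortality?**

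| Variant | Participants at 60% mortality | at 40% mortality |
|---|---|---|
| Schoenfeld, two-sided 0.05, 80% | 127–129 | 190.5–193 |
| Freedman, two-sided 0.05, 80% (81.5 deaths, 82 rounded up) | 136–137 | 204–205 |
| Schoenfeld, one-sided 0.05, 80% | 102 | 153 |
| Schoenfeld, two-sided 0.05, 90% | 172 | 258 |
| Freedman, two-sided 0.05, 90% | 184 | 275 |

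A two-sided level of 0.01 at 80% power with 60% mortality gives 4(2.576 + 0.842)²/0.4120/0.60 ≈ 189. However, the protocol states 0.05 in both Estimated sample size and power and Statistical methods. On the stated level and power, none of these variants reaches 190 with 60% mortality.

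**Step 5: what 190 evaluable participants provide if each is counted to three years.**
- Deaths: 190 × 0.60 = 114.
- Power at 1.9: Φ(√114/2 × ln 1.9 − 1.960) = Φ(1.467) = 92.9%. Freedman gives 91.2%.
- A log-rank simulation (exponential survival, censoring at three years, 10,000 runs) gives 93.0% with 190 participants, and 79.9% with 128 participants and a mean of 76.8 deaths.
- Hazard ratio detectable with 80% power: exp(2 × 2.802/√114) = 1.69.
- For comparison, 40% dying would give 76 deaths and 79.9% power, which is the protocol's claim.

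**Step 6: follow-up beyond three years.** Assume exponential survival, a hazard ratio of 1.9 with 40% average three-year survival, and uniform accrual with everyone followed until three years after the last inclusion. The synopsis dates (first subject 2020, last subject 2026) imply 6 years of accrual; the sample-size section says 8.
- Average probability of death: 80.5% (6 years) or 83.8% (8 years).
- Deaths among 190: 153 or 159.
- Power at 1.9: about 98%.
- Hazard ratio detectable with 80% power: exp(5.603/√153) = 1.57 or exp(5.603/√159) = 1.56.

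**Step 7: the secondary-endpoint calculation.** Comparing 30% with 50% at 80% power and two-sided 0.05 (no continuity correction) needs 93 per arm, 186 in total, and 186/0.95 = 196 with drop-out. This agrees with about 200 and is unaffected by the problem above.

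**The case against.** The strongest defence is that nothing in the trial goes wrong as a result. The error is conservative, 200 participants are enough for the stated target, and the three-year survival calculation supports 200 on its own. The test, the endpoint and enrolment stay as they are. All of that stands. It bears on how serious the error is, not on whether the statement is correct.

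It is also fair to say that the mechanism is inferred. No formula is shown, so a swap of survival and mortality is the likely explanation and not an established fact. The inconsistency does not depend on it: on the stated inputs, 190 is not the number needed for 80% power.

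A reader might infer more than the protocol supports:

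- *That a hazard ratio of 1.9 contradicts 30% versus 50%.* Under proportional hazards those percentages give ln 0.30/ln 0.50 = 1.74. But they are assumptions for a separate binary endpoint, and an effect to be detected need not equal the effect expected. The gap is also small: 1.9 with 40% average survival corresponds to about 28% versus 52%, within 2 percentage points per arm.
- *That the trial would stop too early at 76 deaths.* The protocol has no event target. Final follow-up is defined by time and the interim analysis by 100 inclusions.
- *That a death count such as 114 should now become a target.* That would add an event-driven criterion to a time-driven design, which goes beyond correcting the arithmetic.
- *That a non-significant result would necessarily be misread.* The final estimate and its interval do not depend on the planning hazard ratio.

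**Conclusion.** The power statement for the primary endpoint is wrong as written. On the protocol's own 40% average three-year survival, 80% power at a hazard ratio of 1.9 needs about 127 to 129 evaluable participants (about 136 by Freedman), so the stated 190 is about 50% too high (190/127 = 1.50). Read the other way, the power stated for 190 is too low (80% against about 93%) and the detectable hazard ratio too large (1.9 against 1.69).

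The 93% and 1.69 rest on proportional hazards, an unadjusted analysis, no loss among the 190, and censoring of everyone at three years. The last condition matters because the sample-size section promises at least three years while Time plan says three years. Under follow-up to study end and the assumptions of step 6, the figures become about 98% and 1.56 to 1.57. In either case the correction is in the trial's favour, and it gives no ground for calling the trial too small.

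**What to change.** Keep 200 participants and replace the primary-endpoint justification in Estimated sample size and power with text along these lines:

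> About 76 to 77 deaths are needed for 80% power at a hazard ratio of 1.9 (two-sided 0.05, 1:1 allocation, unadjusted, Schoenfeld). With 40% average three-year survival, that is a 60% probability of death, and each participant counted to three years, 190 evaluable participants give about 114 deaths. This provides about 93% power for a hazard ratio of 1.9 and 80% power for 1.69. Allowing for 5% drop-out, 200 participants will be included.

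Add that these figures are conditional on censoring at three years. If participants are followed to study end, with exponential survival and uniform accrual over 6 to 8 years, about 153 to 159 deaths are expected. Power for 1.9 is then about 98%, and the hazard ratio detectable with 80% power about 1.56 to 1.57. State which follow-up applies to the primary analysis.

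Base any new power calculation for prolongation on the corrected death probability. If 190 came from some other calculation, such as a stricter significance level, the protocol should show it.

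The cost is a wording change in the protocol, carried into the analysis plan where it repeats the figure. Enrolment, follow-up and the analysis are unchanged.

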# BRECLIM

### **Breast Cancer Liver Metastasis**

## A multicentre randomized clinical trial investigating local treatment for breast cancer liver metastasis

Protocol Version	2020-09-14				
	ClinicalTrials.gov Identifier: NCT04079049				
Trial registration	Cancer studies in Sweden (cancercentrum.se) #88154				
Trial funding	Swedish Breast Cancer Association				
Trial funding	Swedish Research Council				
Methodology:	Multiple Center Randomized Clinical Trial				
Study Duration	The planned duration of study participation for an individual				
Study Duration:	subject from inclusion to follow-up are at least 3 years				
	Norrlands University Hospital Umeå				
	Sahlgrenska University Hospital Gothenburg				
Study Centers:	Skane University Hospital Lund				
Study Centers.	Akademiska University hospital Uppsala				
	University Hospital of Linkoping				
	Karolinska University Hospital Huddinge				
Primary Investigator:	[name] (Umeå)				
	[name] (Umeå)				
	[name] (Umeå)				
Study coordinating group	[name] (Umeå)				
	[name] (Göteborg)				
	[name] (Sunderbyn)				
Statistician	[name] (Umeå)				
Data Management	[name] (Stockholm)				
Project coordinator	[name] and [name] (Umeå)				
Study nurse coordinator	[name] (Umeå)				
	[name] (Umeå)				
	[name] (Gothenburg)				
Local Investigators	[name] (Linköping)				
surgery:	[name] (Uppsala)				
	[name] (Stockholm)				
	[name] (Lund)				
	[name] (Umeå)				
	[name] (Gothenburg)				
Local Investigators	[name] (Linköping)				
oncology:	[name] (Uppsala)				
	[name] (Stockholm)				
	[name] (Lund)				
	Representative for surgery				
Safety committee	Representative for oncology				
	Representative for statistics				
Study monitor	Clinical trial unit Umeå				

	Primary endpoint:				
	1. Time to death from any cause				
	Secondary endpoints:				
	1. Three years survival				
	2. Progression free survival				
Objective(s)/ Outcome(s):	3. Median overall survival				
	4. Breast cancer specific survival				
	5. Overall complications				
	6. Quality of life				
Number of Subjects	7. Prognostic factors				
Number of Subjects:	200 patients, 100 in each arm				
	§ 1-4 liver metastasis amendable to surgery with functional				
	liver remnant volume >30%.				
	§ Signed informed consent				
	§ >18 years old				
Inclusion Criteria:	§ ECOG 0-1				

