#### Oncological treatment

Participants in both arms receive oncological treatment. Oncological breast cancer treatment is based on the molecular subtype of the tumour and follows established principles according to the national guideline (3). All participants are discussed at multidisciplinary conferences as in general clinical practice to optimize treatment. Chemotherapy is given for two months while hormonal therapy is given for three months. Those who are stable or respond to treatment are randomized to either surgery followed by oncological treatment or oncological treatment only.

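### The target of 200 is counted at inclusion in the sample-size text and at randomisation elsewhere, with no allowance for patients who progress in between

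*Protocol*

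**What the plan says.** **Counts that point to inclusion.** Estimated sample size and power requires 190 participants for the primary comparison ("to reach a power of 80 % to detect a hazard ratio of 1.9 with a significance level of 0.05, 190 study participants") and then inflates: "Under the assumption of a drop-out rate of 5%, we therefore intend to include 200 participants in total". The accrual forecast in the same section uses the same verb: "We assume that we can include 50% of these, thus 35 per year". The interim analysis, also there and repeated under Project organisation, is triggered once 100 participants have been included.

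**When inclusion happens.** In Table 1 (Variables and measures) the row "Informed consent and inclusion" is marked at the first visit. Randomisation is marked at the second liver surgery MDT, time 0, after the oncological treatment column. Under Oncological treatment, that induction lasts two months for chemotherapy or three for hormonal therapy, and then: "Those who are stable or respond to treatment are randomized to either surgery followed by oncological treatment or oncological treatment only". Progression on oncological treatment is an exclusion criterion.

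**Counts that point to randomisation.** The synopsis gives "200 patients, 100 in each arm", and the population line in the table under Local treatment describes the 200 as patients who are stable or responding. Both describe people who have completed induction.

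No section states an expected progression rate, and the 5% is not said to cover loss before randomisation.

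**The concern.** Inclusion and randomisation are separate events in this protocol, two to three months apart, with a selection step between them. A target, an accrual rate and an interim trigger expressed in inclusions are therefore not interchangeable with a target expressed per arm.

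Two things depend on which count is meant. If recruitment closes at 200 inclusions, as the sample-size text literally says, any progression during induction leaves fewer than 100 per arm, and the power stated for the secondary three-year survival comparison may not be reached. If recruitment closes at 200 randomised, the number is right but the recruitment forecast leaves out the progressors. The interim trigger has the same ambiguity: 100 included is not 100 randomised.

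**Working it through.** **Inputs from the protocol.** 190 required; 5% drop-out; hazard ratio 1.9; 80% power; significance level 0.05, "in a twosided test"; 1:1 allocation; three-year survival 40% averaged over arms; 30% versus 50% for the secondary endpoint; 35 inclusions per year; up to 8 years of recruitment; last subject in planned for 2026 (synopsis).

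**Assumption.** The pre-randomisation loss *a* is not in the documents. I use 10, 20 and 30%.

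**Step 1: reproduce the plan's figures.**
- Target: 190/(1 − 0.05) = 200 exactly. The 5% is fully used.
- Secondary endpoint, normal approximation without continuity correction: 93 per arm, 186 in total, 196 after 5% drop-out. This is close to the stated 200.

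**Step 2: the 200 counted at inclusion.**
- Randomised = 200(1 − a); remaining after drop-out m = 0.95 × 200(1 − a).
- Secondary power, with n = m/2 per arm: Φ{[0.20√n − 1.96√(2 × 0.4 × 0.6)] / √(0.3 × 0.7 + 0.5 × 0.5)}.
- Primary power (Schoenfeld), with deaths by three years D = 0.60m: Φ{√D × ln(1.9)/2 − 1.96}.

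| Loss before randomisation (assumed) | Randomised (per arm) | After 5% drop-out | Power, 30% vs 50% | Deaths by 3 years | Power, HR 1.9 |
|---|---|---|---|---|---|
| 0% | 200 (100) | 190 | 81% | 114 | 93% |
| 10% | 180 (90) | 171 | 77% | 103 | 90% |
| 20% | 160 (80) | 152 | 72% | 91 | 87% |
| 30% | 140 (70) | 133 | 66% | 80 | 82% |

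**Step 3: the 200 counted at randomisation.** Inclusions needed = 200/(1 − a); years = inclusions/35.

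| Loss (assumed) | Inclusions needed | Years at 35 per year |
|---|---|---|
| 0% | 200 | 5.7 |
| 10% | 223 | 6.3 |
| 20% | 250 | 7.1 |
| 30% | 286 | 8.2 |

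The 8-year window yields 8 × 35 = 280 inclusions, so it tolerates a loss of 1 − 200/280 = 28.6%. The synopsis dates, taken generously as seven full years (2020 to 2026), yield 245 inclusions and tolerate 1 − 200/245 = 18.4%.

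**Step 4: the interim trigger.** At 35 per year, 35 × 2/12 ≈ 6 to 35 × 3/12 ≈ 9 of the first 100 included would still be in induction when the trigger is met, even if nobody progressed. Progressors reduce the randomised number further.

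**Step 5: is the inclusion reading realistic?** The 18-month milestone under Specific intermediate objectives expects 50 recruited with complete CRF1. That is about 35 × 1.5 = 52.5, and Table 1 assigns CRF1 to the first visit. Accrual is thus counted before induction. The Ethics section also records that inclusion was moved earlier by amendment.

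**The case against.** The best reply is that *include* in the sample-size section is loose wording for *randomise*. The 190 comes from a two-arm calculation, and allocation applies to those who reach it: "The 1:1 allocation of participants into groups will be performed in random blocks". The synopsis and the population line say outright that the 200 are the randomised patients, and listing progression as an exclusion criterion fits the same reading. Then 100 per arm is met and no sample is lost. This stands as a plausible reading, but it does not settle the matter. Elsewhere the protocol keeps the two events apart (Table 1, the separate CRF2 sections, quality of life measured at inclusion and then timed from randomisation), and the forecast is tied to inclusions.

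Two stronger conclusions are tempting, and the documents support neither.

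- *The trial cannot reach 100 per arm.* This follows only if the count is taken at inclusion and someone progresses. The documents support both counts and give no progression rate, so the size of any shortfall cannot be computed from them.
- *The primary analysis is underpowered.* Under the stated 40% survival, power for a hazard ratio of 1.9 stays at 82% or more across the assumed range. The required 190 is reproduced only if 40% is taken as the share who die (76.2 events/0.40 = 190.5). On that basis primary power would be 76/71/65%. How the 190 was derived is a separate question and not evidence of a shortfall here.

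On accrual, the 5.7 years is my division and not a protocol commitment. The 8-year window absorbs most of the assumed range, and the protocol also leaves room for centres outside Sweden, subject to a further specified protocol and ethical review. For the interim, the trigger is ambiguous, but I have shown no effect on error rates or safety.

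**Conclusion.** The point holds as an unreconciled definition of the 200. As written, the sample-size section would let recruitment close at 200 inclusions, which is inconsistent with 100 per arm as soon as one patient progresses during induction.

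On that reading the loss falls on the secondary three-year comparison, not on the primary comparison under the stated survival. The size rests on the assumed 10 to 30% loss, a further 5% drop-out and, for the primary endpoint, 60% dead by three years. On the other reading the sample size is intact, and what remains is a forecast without a deduction for progressors. That still fits the 8-year window up to about 28% loss, but fits the 2026 last-subject-in date only up to about 18%.

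It deserves correction because it decides when recruitment closes and when the interim analysis is done. It does not show that the design is unworkable.

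**What to change.** 1. In Estimated sample size and power, state that 200 participants will be randomised, 100 per arm, in line with the synopsis and the population line under Local treatment.
2. Count recruitment closure and the interim trigger on randomised patients, and use the same wording for the interim under Project organisation.
3. State an assumed pre-randomisation loss with its basis, derive inclusions needed as 200/(1 − rate), and check the result against both the 8-year window and the 2026 date.
4. If 200 inclusions is the intended cap, state instead the expected number randomised and the resulting power for 30% versus 50%.

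The cost is a wording amendment and a less favourable accrual forecast: at an assumed 20% loss, 250 inclusions and 7.1 years. No treatment rule or analysis method changes.
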